Baseline and follow-up scans: Will include resting state (10 min), cognitive task (Stroop[51, 52]; 10 min), reward task (monetary incentive delay[48, 53, 54]; 10 min), and a transfer task (5 min; see below); collected using a T2* sensitive gradient-recalled single shot echo planar pulse sequence. A high-resolution T1-weighted 3D anatomical scan will be acquired at the baseline scan using a magnetization prepared rapid gradient echo sequence.

Training scans: Subjects will perform five 5-minute runs of active neurofeedback and a 5-minute transfer run before and after the feedback runs. Table 1 summarizes data collection. fMRI data will not be multiband due to the need to reconstruct and process data in real-time.

Other measures: Participants will be given self-report measures of general intellectual function (Shipley Institute of Living Scale[55]), impulsivity (UPPS impulsive behavior scale[56]), negative affect (Quick Inventory of Depressive Symptomatology[57]), craving (Opioid Craving Scale[58]) and withdrawal (Clinical Opiate Withdrawal Scale[59]). As previously noted, these measures may be collected in-person but in an effort to reduce the amount of time participants are physically present at the MRRC we will perform this data collection remotely whenever possible.

Imaging parameters: MRI data will be collected with a 3T Siemens Primsa system and 32-channel head coil. Functional runs will be acquired using an EPI sequence with the following parameters: TR = 2000 ms, TE = 25 ms, flip angle = 90°, acquisition matrix = 64 × 64, in-plane resolution = 3.5 mm², 34 axial-oblique slices parallel to the AC-PC line, slice thickness = 4. Parameters of the anatomical MPRAGE sequence were as follows: TR = 1900 ms, TE = 2.52, flip angle = 9°, acquisition matrix = 256 × 256, in-plane resolution = 1.0 mm², slice thickness = 1.0 mm, 176 sagittal slices. A 2D T1-weighted image coplanar to the functional images was collected for registration.

Connectome-based neurofeedback uses a similar approach to CPM (described above) but summarizes connectivity for a previously defined predictive network, here calculated in real time and used to construct a feedback signal (**Fig 1**).

[figure not shown]

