Fig. 1: Connectome-based neurofeedback: A parcellation used to calculate a connectivity matrix and one or more networks that predict behavior are the inputs. The predictive network(s) defines which edges are used to provide feedback. A connectivity matrix is calculated over a discrete block of data (~1-3 minutes) in real time. Once calculated, the predictive edges are selected from the matrix and summarized into a single network summary score per network. Intermittent feedback is then provided to the subject based on a combination of these network summary scores. The total time from collecting the last volume in the data block to displaying feedback to the subject will be under 1.5 sec (or 1 TR of conventional data).

This approach requires two inputs: a parcellation to calculate a connectivity matrix, and networks (i.e., a collection of edges or elements in the connectivity matrix) to summarize connectivity. The parcellation/networks can be as simple as two ROIs and the single connection between them or can be ~300-400 node parcellations with multiple networks composed of hundreds of edges. When using inputs based on CPM, the parcellation will typically contain ~300 nodes and the positive and negative components will include ~500 edges each. Connectivity will be calculated using 30s blocks of fMRI data collected in real-time. Unlike other approaches using sliding window correlations or continuous feedback [42, 43] the blocks of data will be non-overlapping and feedback will be intermittent. This approach reduces noise in the feedback signal, allows adequate time to calculate the feedback score, and reduces cognitive and attentional load and potential distraction of evaluating continuous feedback[60]. After a matrix is computed, edges will be summarized to a single number reflecting the strength of connectivity in the opioid abstinence network.

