Processing pipeline: Data will be motion corrected with our validated rt-fMRI motion correction algorithm[61]. Data cleaning will include linear and quadratic drift removal; regression of cerebrospinal fluid, white matter and global signals; calculation and removal of a 24-parameter motion model (6 motion parameters, 6 temporal derivatives and their squares)[62]; motion censoring[63]; and low-pass filtering via temporal smoothing with a Gaussian filter. Connectivity will be calculated using Pearson correlation. As connectivity is very sensitive to head motion[64], we include two types of motion censoring to remove confounding effects of motion on connectivity and the resulting feedback signal. For each frame, we will calculate the frame-to-frame displacement as defined in[64]. Frames with motion >0.15mm and the two frames immediately before and after (to account for temporal smoothing) will be excluded. We will also censor whole blocks of feedback if a large number of frames (e.g., 10%) have been censored. These features minimize the likelihood of subjects receiving feedback mainly reflecting motion artifacts. After calculating connectivity for all predefined nodes, edge strength for all connections in the predefined network will be summarized in the same manner as Step 2 in CPM (**see Connectome-based predictive modeling**, above)[31]. The feedback signal will be the overall strength of the opioid abstinence network. For data harmonization, imaging data collected at baseline and follow-up scans will be processed (off-line) in the same manner as the neurofeedback data.

Neurofeedback and transfer runs: Feedback and transfer runs will consist of 30 sec blocks during which subjects try to increase connectivity in the opioid abstinence network. During feedback runs, subjects in the active feedback group will be given feedback as the difference between positive and negative edges: feedback = $\sum_{edges} r(\text{positive edges}) - \sum_{edges} r(\text{negative edges})$. Feedback will be presented as a bar graph with hot colors for positive differences and cool colors for negative differences (similar to **Fig 1**). Subjects will be instructed to increase the feedback bar (i.e. increase overall network strength), as indicated by a green arrow pointing up for 30 sec, and feedback will be presented intermittently

IRB# 2000025618

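### Does a 15-frame feedback block leave too few data for the 29 cleaning terms the plan removes?

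*Combined protocol and SAP*

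**What the plan says.** The relevant text is all in Section I.4, Research Plan, of the combined protocol and SAP.

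- *Imaging parameters* and *Training scans*: functional runs have a TR of 2000 ms, without multiband.
- *Connectome-based neurofeedback*: "Connectivity will be calculated using 30s blocks of fMRI data collected in real-time". The blocks do not overlap. *Neurofeedback and transfer runs* repeats the 30-second block and adds a 10-second feedback display.
- *Fig. 1 legend*: "A connectivity matrix is calculated over a discrete block of data (~1-3 minutes) in real time".
- *Processing pipeline*: cleaning includes "linear and quadratic drift removal; regression of cerebrospinal fluid, white matter and global signals", then "calculation and removal of a 24-parameter motion model (6 motion parameters, 6 temporal derivatives and their squares", then motion censoring and Gaussian temporal smoothing. Pearson correlation gives connectivity.
- Censoring, same paragraph: "Frames with motion >0.15mm and the two frames immediately before and after (to account for temporal smoothing) will be excluded". Then: "We will also censor whole blocks of feedback if a large number of frames (e.g., 10%) have been censored".
- Off-line data, same paragraph: "imaging data collected at baseline and follow-up scans will be processed (off-line) in the same manner as the neurofeedback data".
- *Training scans*: "Subjects will perform five 5-minute runs of active neurofeedback and a 5-minute transfer run before and after the feedback runs".

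No sentence says which frames the cleaning regression is fitted to (block, run so far, whole run or session), or whether its terms enter jointly or in steps.

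**The concern.** The block is the only unit of data that the text links directly to computing the feedback, so a reader may assume that cleaning is done within it. On that reading there are more regressors than frames. The regression reproduces every time series exactly, the residuals are zero, and a Pearson correlation of them is undefined or is rounding error.

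The feedback bar is the intervention, so a bar without signal would mean that nothing was trained. The sentence on off-line processing could carry the problem into the outcomes: resting and task connectivity for Aim 2, and the change in transfer-run connectivity for H3b. The block length in the figure legend differs from the text. The example limit for dropping a block also looks very tight for 15 frames.

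**Working it through.** **The plan's own figure.** 6 motion parameters + 6 derivatives = 12; with their squares, 12 x 2 = 24. This agrees with the text.

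**Columns.** 24 + 3 (cerebrospinal fluid, white matter, global) + 2 (linear, quadratic drift) = 29; with an intercept, 30. If the motion model is a separate step, 24 + 1 = 25.

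**Frames.** Frames = duration / TR, with TR = 2 s. Residual df = frames - columns, not below zero.

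| Fitting window | Frames | df, joint model (30) | df, motion step (25) |
|---|---|---|---|
| 30-s block | 15 | 0 | 0 |
| 1 min (low end of legend) | 30 | 0 | 5 |
| 2 min | 60 | 30 | 35 |
| 3 min (high end of legend) | 90 | 60 | 65 |
| 5-min run | 150 | 120 | 125 |
| 10-min rest or task run | 300 | 270 | 275 |

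A least-squares check on simulated noise with simulated motion traces gave rank 15 at 15 frames. The residual share of variance was about 1e-29 for the joint model and 1e-30 for the motion step alone, which is zero to rounding. A fit within the block is therefore impossible, whether joint or stepwise.

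**Fit on the current run so far.** The documents give no run timeline. Assume cycles of 30 s + 10 s and no lead-in. Block *k* then ends at 15 + 20(*k* - 1) frames.

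- Block 1: 15 frames, 0 df.
- Block 2: 35 frames; 35 - 30 = 5 df jointly, or 35 - 25 = 10 df for a separate motion step.
- Block 3: 55 frames; 25 or 30 df.
- Block 7: 135 frames; 105 or 110 df.
- Lead-in *L* for at least 1 df at block 1: 15 + *L* - 30 >= 1 gives 16 frames (32 s); 15 + *L* - 25 >= 1 gives 11 frames (22 s).

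**Fit from the pre-feedback transfer run onward.** 150 + 15 = 165 frames at the first feedback block; 165 - 30 = 135 df. Separate intercept and drift terms for the second run add 3 columns: 165 - 33 = 132 df. This uses only scans already scheduled.

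**Off-line data.** Transfer runs are 5 minutes and the resting, Stroop and reward runs 10 minutes each. Whole-run fits leave 120 and 270 df. The Aim 3 approach in *Hypothesis testing* takes connectivity over transfer runs and does not mention blocks.

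**Censor limit.** 10% of 15 = 1.5 frames. One in-block exceedance removes 2 to 5 frames, depending on its position and on how many neighbours are dropped each side: 2/15 = 13% to 5/15 = 33%. Such an event would drop the block. The 10% is given only as an example, and the paragraph states its aim of keeping motion artefact out of the feedback.

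**The case for a change.** The strongest case for acting is that the plan specifies the regressors, the displacement threshold and the censoring, yet omits the one choice on which the existence of a signal depends. One natural reading (the block) is impossible. Another (the run so far) fails at the first block unless there is lead-in, and none is described. A whole-run fit is not available while the run is in progress. Software may still return a correlation computed from rounding error, so a bar could appear with nothing behind it. One added sentence would close the gap.

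Much of this stands. The window is not stated, the per-block reading cannot work, and the legend and text give different block lengths.

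It does not establish a defect. The 30-second block is attached to the correlation step. Cleaning is described separately and includes temporal smoothing and removal of neighbouring frames, which apply naturally to a continuous series. A team building the system must choose a window before it can run, and residuals at 1e-29 of the original variance would show up in the first test. The legend describes the method in general terms, while two study-specific statements give 30 seconds.

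Nor can the effect on the intervention be sized. A count of affected blocks would need the run timeline. Chance variation in a single edge does not measure noise in a bar that sums roughly 500 positive and 500 negative edges.

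Prescribing a window has its own cost. A session-cumulative fit in real time with a whole-run fit off-line would clean the trained signal and the outcome data differently, despite the plan's wish to harmonise them. Some difference of this kind is hard to avoid, because a complete run is never available in real time.

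**Conclusion.** No change to the plan follows. The arithmetic is certain: 15 frames against 24 motion terms, or 29 cleaning terms, leaves 0 residual df if the fit is confined to one block. The plan does not state that fit, and workable windows lie within the existing schedule, with 120 df for a 5-minute run, 270 df for a 10-minute run and 135 df from the transfer run onward. This is a technical detail left out of a section whose template asks for non-technical language, and the people running the pipeline have to fill it.

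The conclusion assumes that the implemented software cleans over more than one block. The documents neither confirm nor contradict this. The choice among workable windows could affect noise and residual motion in the feedback, but the documents give no motion rate or run timeline from which to size that. The legend's block length is a loose general description, and the censor limit is an illustrative and deliberately protective figure. No bias of any planned test is shown.

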We will utilize connectome-based neurofeedback to assess patterns of functional connectivity within a previously identified “opioid abstinence network”. This network was identified using a whole-brain machine learning approach and predicted subsequent opioid relapse among methadone-maintained individuals. This network was robust, relatively unchanged in follow-up analyses controlling for other clinical variables (e.g., methadone dose, years of opioid use), predicted opioid relapse from different fMRI tasks as well as resting state, and predicted opioid use at multiple time points (two scanning sessions conducted 3 months apart). Design: Individuals on methadone (N=24) will receive active (n=24) connectome-based neurofeedback at 3 weekly scanning sessions (training scans 1-3). Training scans will include both feedback and transfer (i.e. no feedback) runs. Baseline (one week prior to training scan 1) and follow-up (one week following training scan 3) scans will be conducted to test the effects of feedback training on intrinsic connectivity during resting state and fMRI tasks, as in our pilot data. Clinical features of OUD (opioid use, craving, negative affect) will be assessed weekly and at one month follow-up.

Aim 1. To determine if connectome-based neurofeedback is associated with reduced opioid use. Aim 1a. We predict that individuals who receive active feedback will report lower

IRB# 2000025618

levels of opioid use from baseline to follow-up scans. *Aim 1b*. We predict that this reduction will persist over time as assessed at 1-month follow-up.

Aim 2. To determine if connectome-based neurofeedback is associated with changes in intrinsic connectivity. *Aim 2a*. Based on evidence that neurofeedback induces changes in intrinsic connectivity[13], we predict that subjects receiving active feedback will show increased opioid abstinence network connectivity during resting state at follow-up versus baseline scans. *Aim 2b*. We predict that this effect will generalize to increased connectivity during fMRI reward and cognitive tasks at these timepoints.

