We plan to enroll twenty-four individuals (12 male, 12 female) receiving methadone for OUD. Eligibility criteria: (i) non-methadone opioid positive urine screen (as assessed during standard treatment at APT) or indicated via Utox or self-reported past-month opioid use at screening); (ii) DSM-5 criteria for OUD, as assessed via structured clinical interview (SCID)[66]; (iii) ≥ 3 months of methadone treatment; (iv) eligibility for MRI; (v) age 18-50; (vi) baseline scanning with acceptable motion (i.e., <.15mm frame-to-frame displacement), as in prior work. Retention: APT patients attend clinic on a daily basis to receive methadone and this has contributed to high retention rates (e.g., 86% over three months) in our studies[10, 67] in this population.

7. **Subject classification:** Check off all classifications of subjects that will be specifically recruited for enrollment in the research project. Will subjects who may require additional safeguards or other considerations be enrolled in the study? If so, identify the population of subjects requiring special safeguards and provide a justification for their involvement.

 Children	 Healthy	 Fetal material, placenta, or dead fetus
 Non-English Speaking persons	 Prisoners	 Economically disadvantaged
 Decisionally Impaired fetuses	 Employees	 Pregnant women and/or
 Yale Students	 Females of childbearing potential	

NOTE: Is this research proposal designed to enroll children who are wards of the state as potential subjects?

Yes No

8. **Inclusion/Exclusion Criteria:** What are the criteria used to determine subject inclusion or exclusion?

Write here

- i. Inclusion criteria
 1. non-methadone opioid positive urine screen (as assessed during standard treatment at APT) or indicated via Utox or self-reported past-month opioid use at screening
 2. DSM-5 criteria for opioid use disorder, as assessed via structured clinical interview (SCID)
 3. ≥ 3 months of methadone treatment
 4. Age 18 to 50
- ii. Exclusion criteria
 1. Meet DSM-5 psychiatric classifications for lifetime schizophrenia or bipolar disorder with psychotic features, or exhibit significant current suicidal or homicidal plans and intent such that hospitalization is required

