 2. Failure to pass an MRI screening
 3. Women who are pregnant or nursing
 4. Baseline scanning with excessive motion based on frame-to-frame displacement

9. How will **eligibility** be determined, and by whom? *Write here*

Participants will be recruited via clinician referrals from the APT Foundation, one of the largest methadone providers in CT, consistent with our prior[10, 48] and ongoing work. In

IRB# 2000025618

addition to regular attendance for methadone, APT patients meet regularly with clinicians, as per federal guidelines. As [name] (Co-I) is Director of Research for the APT, he is ideally suited to facilitate participant referral and longitudinal clinical assessment for this study.

Individuals will be informed about the study by their clinician at their regular APT clinic visits and provided with verbal information and brochures containing project information. Interested individuals will contact the study team and set up a screening visit. At the screening visit, eligibility will be determined by members of the research team.

10. Risks: Describe the reasonably foreseeable risks, including risks to subject privacy, discomforts, or inconveniences associated with subjects participating in the research.

Write here

- i. Potential risks: This protocol presents minimal risks to subjects. Possible risks include:
 1. Magnetic resonance imaging: MRI is a non-invasive procedure with minimum anticipated discomfort and a safety screening process. Prior studies have not found any adverse effects of MRI. The possible risks and discomforts of MRI are as follows:
 - a. Claustrophobia
 - b. Acoustic noise
 - c. Metal implants are a risk within the magnetic MRI environment
 - d. Discomfort lying in the MRI scanner
 - e. Very slight warming of the body, tingling or involuntary muscle twitches
 - f. Unknown risk to a fetus
 2. Behavioral assessments: These are all non-invasive and should add no risk. The major disadvantage will be the time taken to complete the questionnaires. Our past experience with these and related measures indicates that they are acceptable to subjects including individuals with substance use disorders.
 3. Urine toxicology test and its result: This is non-invasive and should add no risk. Our past experience indicates that urine screens are acceptable to subjects including individuals with substance use disorders.

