The statistical tests will be as follows: Aim 1: Opioid use will be entered into a linear effects model with the between-subject factor of feedback group (active/sham). Aim 2: Opioid abstinence network strength during resting state and task fMRI runs will be compared between time points using linear mixed models with the between-subject factor of group (active/sham) and the within-subject factor of time (baseline/follow-up scan). Aim 3: Craving and negative affect will be compared using linear mixed effects model with the between-subject factor of group (active/sham) and the within-subject factor of time (baseline/follow-up scan). Associations between craving and negative affect and opioid abstinence network connectivity strength during transfer runs will be tested using Pearson's or Spearman's correlations, as appropriate depending on the distribution of the data. Replication: For replication of our pilot data (Figure 2 of research strategy), Pearson's correlations will be tested between opioid abstinence network connectivity strength at baseline and percent opioid-negative urines across the study.

SECTION II: RESEARCH INVOLVING DRUGS, BIOLOGICS, RADIOTRACERS, PLACEBOS AND DEVICES

If this section (or one of its parts, A or B) is not applicable, check off N/A and delete the rest of the section.

A. RADIOTRACERS N/A

B. DRUGS/BIOLOGICS N/A

C. DEVICES N/A

SECTION III: RECRUITMENT/CONSENT AND ASSENT PROCEDURES

1. Targeted Enrollment: Give the number of subjects:

- a. Targeted for enrollment at Yale for this protocol:
24 completers (individuals participating in all scanning sessions).
- b. If this is a multi-site study, give the total number of subjects targeted across all sites: NA

2. Indicate recruitment methods below. Attach copies of any recruitment materials that will be used.

 Flyers	 Internet/web postings	 Radio
 Posters	 Mass email solicitation	 Telephone
 Letter	 Departmental/Center website	 Television
 Medical record review*	 Departmental/Center research boards	 Newspaper
 Departmental/Center newsletters	 Web-based clinical trial registries	 Clinicaltrials.gov

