 YCCI Recruitment database	 Social Media (Twitter/Facebook):	
 Other:		

IRB# 2000025618

We plan to collect full data from twenty-four individuals (12 M, 12 F) receiving methadone for OUD. Thus, in order to account for possible participant attrition, we will likely scan up to 40 individuals (and anticipate screening up to 100). Participants will be recruited via clinician referrals from the APT Foundation, one of the largest methadone providers in CT, consistent with our prior[48, 49] and ongoing work. While rates of other forms of medication-assisted treatment (e.g., buprenorphine, naltrexone) have increased in recent years, methadone remains the most prevalent treatment for OUD in the US[20], therefore, to reduce sample variability, this study will only recruit individuals treated with methadone. For regular attendance for methadone, APT patients meet regularly with clinicians, as per federal guidelines. [name] (Co-I), Director of Research for APT, is ideally suited to facilitate participant referral and longitudinal clinical assessment for this study.

* Requests for medical records should be made through JDAT as described at
<http://medicine.yale.edu/ycci/oncore/availableservices/datarrequests/datarrequests.aspx>

3. Recruitment Procedures:

- a. Describe how potential subjects will be identified. *Write here*
- b. Describe how potential subjects are contacted. *Write here*
- c. Who is recruiting potential subjects? *Write here*

Consistent with previous studies conducted by the PI and co-investigators, participants in methadone treatment for an opioid-use disorder will be recruited from the APT Foundation. Interested participants entering the methadone treatment program at APT will be referred by APT personnel to research staff when possible for eligibility screening. [name], a co-investigator for this study, is both the Director of Research and the Director of Pain Services for the APT Foundation, he is ideally suited to facilitate participant referral and longitudinal clinical assessment for this study. Participants may also be referred to the study by word of mouth from other participants. HIC approved recruitment materials will provide information about how to contact research staff to learn more about the study. All recruitment will be conducted by local HIC-approved study personnel who completed HIC training requirements.

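### Does the motion-censoring rule leave the delivery of feedback so uncertain that the plan must change?

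*Combined protocol and SAP*

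**What the plan says.** The rules are in Section I, 4 (Research Plan). Imaging parameters gives a TR of 2000 ms. The paragraph on connectome-based neurofeedback says: "Connectivity will be calculated using 30s blocks of fMRI data collected in real-time". The Processing pipeline paragraph has two layers of motion censoring. For frames: "Frames with motion >0.15mm and the two frames immediately before and after (to account for temporal smoothing) will be excluded". For blocks: "We will also censor whole blocks of feedback if a large number of frames (e.g., 10%) have been censored". It gives the purpose as keeping participants from being shown feedback that is mostly motion artifact.

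On eligibility, Section I, 6 (Subject Population) requires "baseline scanning with acceptable motion (i.e., <.15mm frame-to-frame displacement), as in prior work". The matching exclusion in Section I, 8 has no number: "Baseline scanning with excessive motion based on frame-to-frame displacement".

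On numbers, Section I, 1 states: "Individuals on methadone (N=24) will receive active (n=24) connectome-based neurofeedback at 3 weekly scanning sessions (training scans 1-3". Section III, 1 (Targeted Enrollment) sets the target at "24 completers (individuals participating in all scanning sessions", and Section III, 2 adds, to allow for attrition, "we will likely scan up to 40 individuals (and anticipate screening up to 100".

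The Fig. 1 caption describes blocks of roughly 1 to 3 minutes and equates 1.5 seconds with one conventional TR. Neither matches the 30-second, 2-second-TR text.

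**The concern.** The displayed bar is the intervention. If one small movement cancels a block, a participant who passes the motion screen and attends every session could see little feedback and still count among the 24. A null result in Aims 1 to 3 could then mean that feedback does not work or that it was not delivered.

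The eligibility limit does not rule this out. Read as a mean, it says little about how many single frames exceed 0.15 mm. Read as a limit on every frame, it is very demanding at baseline but says nothing about the three training scans. The documents set no minimum number of displayed blocks and do not say what appears on screen when a block is dropped.

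**Working it through.** The plan states no expected share of blocks kept or lost, so there is no figure of its own to reproduce on this point. Its power statement does not bear on it.

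**One moved frame.** Frames per block = 30 s / 2 s = 15, and 10% of 15 = 1.5 frames, so two censored frames exceed the threshold. The phrase about the two neighbouring frames can mean two on each side or one on each side.

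| Reading | Frames censored by one moved frame in the block | Share of 15 | Block lost? |
|---|---|---|---|
| Two each side | 3 to 5 | 20.0-33.3% | at all 15 positions |
| One each side | 2 to 3 | 13.3-20.0% | at all 15 positions |
| Neighbours not counted | 1 | 6.7% | no; two moved frames needed |

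With two each side, a moved frame immediately outside the block also takes 2 of 15 frames (13.3%) and cancels it. The third reading is less natural, because the text presents frame exclusion, neighbours included, as one of its two types of censoring.

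**Dependence on block length.** At TR 2 s with two neighbours each side, one moved frame inside the block censors:

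- 60 s (30 frames): 3/30 to 5/30 = 10.0-16.7%
- 120 s (60 frames): at most 5/60 = 8.3%
- 180 s (90 frames): at most 5/90 = 5.6%

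At the 2 to 3 minute end of the Fig. 1 range a single frame cancels nothing. If the caption's 1.5 s were the TR, a 30-s block would have 20 frames. One moved frame would then censor 15-25% (two each side) or 10-15% (one each side).

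**Blocks kept.** Assume that a share p of frames exceeds 0.15 mm, independently. A block survives with probability (1-p)^17 x (1-p^2) for two each side, and (1-p)^15 x (1-p^2) for one each side. The last factor covers a moved frame near both ends at once. If neighbours do not count, it is (1-p)^15 + 15p(1-p)^14.

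| p | Two each side | One each side | Neighbours not counted |
|---|---|---|---|
| 1% | 84.3% | 86.0% | 99.0% |
| 5% | 41.7% | 46.2% | 82.9% |
| 10% | 16.5% | 20.4% | 54.9% |

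The number of planned blocks is also open. A 5-minute run holds 7 whole blocks if the 10-s display follows each 30-s block (300/40 = 7.5), or 10 if the display falls inside it. Over 5 runs and 3 scans that is 105 or 150.

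**What the eligibility limit implies.** If it is a mean, Markov's inequality bounds the share of frames above 0.15 mm only by mean/0.15, for example 0.10/0.15 = 67%. Simulation with gamma or lognormal displacement, coefficient of variation 0.5 to 1.0, lag-1 correlation 0 to 0.8 and both neighbour readings gives 42-98% of blocks kept at a mean of 0.05 mm, 1-42% at 0.10 mm and 0-13% at 0.149 mm. These ranges come wholly from the assumed distributions. If the limit applies to every frame, the 35 baseline minutes (10+10+10+5), or 1,050 volumes, must all be clean. The ratio 24/40 does not turn this into a rate for the training scans, because people differ in motion and the 40 also covers other attrition.

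**What loosening would buy and cost.** Dropping a block only when more than 5 of 15 frames are censored would keep 98.7%, 78.9% and 47.9% at p = 1%, 5% and 10% (two each side). In the same simulation at a mean of 0.10 mm it keeps 8-72%, against 1-42%. The price is more residual motion and a noisier correlation: the nominal Fisher-z standard error per edge is 1/sqrt(15-3) = 0.29 with 15 frames and 1/sqrt(10-3) = 0.38 with 10.

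**What is already collected.** Displacement is computed for every frame (Processing pipeline), so the blocks that passed can be counted for each participant and session. Each training scan has a transfer run before and after the feedback runs (Training scans), which tests control without feedback. After each scan participants are asked whether they felt able to control the feedback (Neurofeedback and transfer runs).

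**The case for a change.** The strongest case for a change is that one undefined word moves delivered feedback from nearly all to possibly almost none, that the sample is only 24, and that the remedy is cheap: define the eligibility statistic, state the block rule in frames, log displayed blocks, and repeat the analysis in those above a preset minimum. It can add that 10% is the only value offered, and that with two neighbours each side a single frame stops cancelling blocks at every position only at a threshold of at least 5/15 = 33%.

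The arithmetic stands, and so does the observation that delivery is not quantified. The step to a required change does not. The 10% is an example attached to the idea of a large number of frames, so the operators may set another value. A looser rule weakens a safeguard whose purpose is stated. Baseline and follow-up images are to be processed in the same manner, so if the block rule is part of that, loosening it would let more motion into the outcome measures too. The attendance count is an enrolment target; no text makes it the analysis set. A minimum-delivery subset would be a sensitivity analysis beside an unchanged main analysis, and the count it needs can be made from existing output.

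**Conclusion.** No change to the plan is needed. At the example threshold, one frame above 0.15 mm cancels a 30-s block. This assumes a 2-s TR and that excluded neighbours count as censored, and it fails at block lengths of 2 to 3 minutes. The resulting loss cannot be computed from the documents. Across assumed shares of 1% to 10% of moved frames, blocks kept run from about 86% down to about 17%, and nothing in the documents says where participants will lie.

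The strict threshold is a fair trade-off between motion artifact and delivered feedback, and it is the investigators' choice. The open details are the block threshold in frames, the eligibility statistic, the screen shown for a dropped block, and the volumes used to estimate nuisance regressors in real time. The team running the pipeline must settle these in any case and can do so without touching the aims or the main analysis. The mismatch between the Fig. 1 caption and the text is clerical and should be reconciled. Reporting displayed blocks per participant would help a reader interpret a null result, and the displacement data already support it.
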